9. STUDY DISCONTINUATION AND PARTICIPANT DISCONTINUATION/WITHDRAWAL

9.1 DISCONTINUATION OF STUDY SITE OR STUDY

The Sponsor has the right to terminate the study at any time. Reasons for site discontinuation include:

- Conduct of the study is not in accordance with the GCP guidelines
- Repeated failure to complete documentation (source documents or eCRFs) / quality of data
- Failure to obtain Informed Consent
- Failure to report Serious Adverse Events (SAEs) within 24 hours of knowledge
- Repeated protocol deviations
- Failure to enroll an adequate number of subjects

The Study Sponsor also reserves the right to discontinue the entire study. Reasons the entire study could be discontinued include, but are not limited to:

- SAEs or if special circumstances concerning the eYST intervention or the company itself occur, making further treatment of subjects impossible

In the event of site or study discontinuation, the study investigator(s) will be informed of the reason for study termination. Study materials must be returned, disposed of or retained as directed by the Study Sponsor.

9.2 PARTICIPANT DISCONTINUATION/WITHDRAWAL FROM THE STUDY

Participants (patients, parents, or support adults) may voluntarily withdraw from the study at any time. Patients may notify the study clinician by calling the phone number(s) listed on the informed consent document. Support adults may do the same or contact the YST-Is. An exit interview to gather information about their experience with study may be conducted. Participants may be withdrawn from the study by the PI if they are unable to be contacted (lost to follow-up), become incarcerated or incapacitated, or are determined to be adversely affected by the program.

10. SAFETY

10.1 SAFETY HYPOTHESIS

eYST is safe for use by individuals with a previous history of suicidal ideation and attempts and their support network (i.e., parents and nominated adults).

10.2 ADVERSE EVENTS

Adverse Events (AEs) will be monitored and documented at each study visit. Reporting of AEs will follow Michigan Medicine Institutional Review Board Policy and NIMH policy. Given that all enrolled participants will have a history of suicidal ideation with plan, AEs related to suicidal thoughts/behaviors will be categorized as “expected”.

10.3 RATIONALE FOR IDENTIFICATION OF ADVERSE CLINICAL EVENTS

The proposed study protocol is based on previous trials of YST. Anticipated adverse clinical events are therefore derived from these previous trials. The YST developers have observed the following adverse events in their studies:

- suicidality
- suicidality-related hospitalization

10.4 EXPECTED ADVERSE EVENTS IN PARTICIPANTS

Given that all enrolled patient participants will have a history of suicidal ideation with plan, AEs related to suicidal thoughts/behaviors will be categorized as “expected”.

Therefore, primary anticipated events include:

- increased suicidal ideation and behavior
- suicide-related hospitalization

Any study participation related adverse events are to be followed until there is evidence of resolution or permanent change.

PROPRIETARY AND CONFIDENTIAL

Oui Therapeutics, Inc. | [name]

The determination of whether an adverse event is classified as a SAE is based on the definitions below, taking into account the clinical judgment of the investigator.

10.5 SERIOUS ADVERSE EVENTS

AEs meeting any of the following criteria will be categorized as “Serious”:

- results in death
- is life-threatening (places the subject at immediate risk of death from the event as it occurred)
- requires inpatient hospitalization or prolongation of existing hospitalization
- results in a persistent or significant disability/incapacity
- results in a congenital anomaly/birth defect
- an important medical event, based upon appropriate medical judgment, may jeopardize the subject’s health and may require medical or surgical intervention to prevent one of the other outcomes listed in this definition, or
- results in a severely debilitating situation for the subject, such as psychological distress, financial hardship or damaging impact on social standing or employability

Suicidal behavior is an expected outcome of preexisting psychiatric illness. Suicidal behaviors that occur as a result of preexisting psychiatric illness will not be classified as an SAE unless they are associated with the use of the eYST website and also meet the SAE criteria listed above.

Important medical events that may not result in death, be life-threatening, or require hospitalization may be considered serious when, based upon appropriate medical judgment, they may jeopardize the participants’ ability to participate and may require medical or surgical intervention to prevent one of the outcomes listed in this definition.

Planned hospitalization for a pre-existing condition, or a procedure required by the protocol, without serious deterioration in health, is not considered a SAE.

A SAE may or may not be considered related to study participation.

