10.6 REPORTING OF ADVERSE EVENTS

AEs which are unexpected, related, and serious will be reported to the Michigan Medicine IRB within 7 calendar days and to the NIMH PO within 10 business days. Death related to the study will be reported to the NIMH PO within 5 business days. All other AEs will be documented and reported to Michigan Medicine IRB and NIMH PO at the time of the respective annual progress reports.

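### Section 10.5 lets attribution to illness remove a suicide attempt from the SAE class, and the blanket expected label leaves a related, serious, non-fatal attempt without an expedited report under 10.6

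*Combined protocol and SAP*

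**What the plan says.** Section 10.5 lists outcomes that make an AE serious. Any one is enough. The list includes death, a life-threatening event, and an event that "requires inpatient hospitalization or prolongation of existing hospitalization". The section ends: "A SAE may or may not be considered related to study participation". In between, it says that suicidal behaviors resulting from preexisting psychiatric illness "will not be classified as an SAE unless they are associated with the use of the eYST website" and also meet the outcome list. Both conditions must hold.

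Section 10.4 makes the SAE decision by these definitions, "taking into account the clinical judgment of the investigator". Sections 10.2 and 10.4 both state that "AEs related to suicidal thoughts/behaviors will be categorized as" expected, without limit by seriousness or relatedness.

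Section 10.6 sets three routes:

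- "AEs which are unexpected, related, and serious will be reported to the Michigan Medicine IRB within 7 calendar days", and to the NIMH program official within 10 business days.
- Study-related death goes to the NIMH program official within 5 business days.
- Everything else goes into the annual progress reports.

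Outside 10.6, section 9.1 lists failure to report SAEs within 24 hours as a ground for discontinuing a site, and names no recipient. Section 10.2 adds: "Reporting of AEs will follow Michigan Medicine Institutional Review Board Policy and NIMH policy". The content of those policies is not in the document.

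**The concern.** Seriousness, relatedness and expectedness are three separate judgments. Section 10.5 merges the first two for one class of event, and 10.6 combined with the expected label lets the third override the other two.

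The class affected is the one the protocol itself anticipates: 10.3 names suicidality and suicidality-related hospitalization as the adverse events seen in earlier YST trials. Section 10.1 states a safety hypothesis for this population. If an SAE count were offered in support of it, attempts that met a listed outcome but were put down to illness would not be in the count. In addition, the IRB could first learn of a related, serious, non-fatal attempt by a minor in an annual report.

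**Working it through.** No arithmetic in the plan is in question. The check traces suicidal events through 10.4 (expected?), 10.5 (SAE?), 9.1 (24 hours?) and 10.6 (which route?).

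**Step 1: the exclusion in 10.5.** Take an attempt attributed to preexisting illness, not linked to the website, that needs admission.

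- Outcome list: met, so the event is serious.
- Closing sentence of 10.5: relatedness is not required.
- Exclusion: "Suicidal behaviors that occur as a result of preexisting psychiatric illness will not be classified as an SAE", and the website exception does not apply, so it is not an SAE.
- Section 9.1: the 24-hour expectation attaches to SAEs, so it does not reach this event.
- Section 10.6: if the event is judged unrelated, it goes to the annual report whether or not it is an SAE.

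The exclusion therefore changes SAE status, the 24-hour expectation and any SAE count. For unrelated events it does not change the route in 10.6.

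Two boundaries are undefined. No rule says when an attempt results from preexisting illness. Aim 2 inclusion criterion 2 admits psychiatric inpatients with an attempt, or with ideation and a plan, so illness is an available explanation for all 20 planned youth. That restates the entry criterion; it is not an event count. Also, the exception names only the website. An attempt attributed wholly to contact with a support adult or intervention specialist is outside the exclusion, and the outcome list applies to it. An attempt attributed to illness together with such contact is not addressed.

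**Step 2: the expected label and 10.6.** The expedited route needs unexpected AND related AND serious. For a non-fatal suicidal event:

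| Related | Serious | Route with the expected label | Route if the same event were unexpected |
|---|---|---|---|
| Yes | Yes | Annual report | IRB 7 calendar days; NIMH 10 business days |
| Yes | No | Annual report | Annual report |
| No | Yes | Annual report | Annual report |
| No | No | Annual report | Annual report |

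With the label, 0 of 4 combinations reach the expedited route. Without it, 1 of 4 does. The label changes exactly one class: related and serious. For that class, 7 calendar days (IRB) or 10 business days (NIMH; two working weeks, so 14 calendar days without holidays) becomes the next annual report. If 10.5 leaves the event an SAE, the 24-hour expectation in 9.1 still applies, but 10.6 has no matching step.

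**Step 3: deaths.** A study-related death reaches the NIMH program official in 5 business days whatever its expectedness. Section 10.6 has no separate IRB clause for death, and the document does not say whether completed suicide falls under the label. If it does, 10.6 gives no 7-day IRB report.

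**Step 4: how the two parts interact.** Section 10.6 tests whether an event is serious, and it is unclear whether an event that 10.5 removes from the SAE class still counts as serious there. Correcting the label alone could leave mixed-cause events outside the expedited route, so both need correcting together.

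**The case against.** The strongest reply is that 10.5 is a general rule followed by a specific, reasoned exception. In acutely suicidal inpatients, some relief from SAE paperwork for events judged unrelated is a defensible choice. This stands in part: the exception is deliberate, and by itself it alters no 10.6 route for unrelated events. It still sits badly beside the section's own outcome list and closing sentence, and it does not spare even fatal cases.

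Second, the events are not lost. AEs are collected from consent to study exit (10.7) and documented (10.6). The C-SSRS is given at Weeks 0 and 12, Appendix B refers to attempts since baseline, and the Cornell Services Index covers inpatient hospitalization. Suicidal behavior and service use are planned exploratory outcomes (3.2, 12.1.5). Appendix B's risk response does not depend on SAE status. All of this stands. It means the counts can be produced from data already planned, but it does not supply a prompt report to the IRB or NIMH.

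Third, the policies cited in 10.2 may impose shorter timelines. That cannot be checked here, so the conclusion is confined to the text of 10.6. Investigator judgment may also help in individual cases, but it is exercised on the definitions at issue.

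A reader might infer that all of Aim 2 could pass between two annual reports: 20 youth / 4 per month = 5 months, plus 12 to 14 weeks (2.8 to 3.2 months), gives 7.8 to 8.2 months, which is under 12. The document does not support this. It gives no report dates, and IRB and NIMH cycles may differ. If the NIMH cycle ran from project month 1 of the 18-month timeline in Appendix A, Aim 2 would have to start by about month 3.8 to 4.2 (12 minus 8.2 or 7.8) to finish before month 12. Before it come 90 days of interviews and wireframes, up to 90 days of partly overlapping build, and start-up. Starting after month 12 leaves only 6 months. On that assumption, a report would very probably fall within Aim 2.

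**Conclusion.** The point holds, within limits. Section 10.5 makes SAE status for illness-attributed suicidal behavior turn on cause instead of outcome. Separately, the expected label removes the expedited report in 10.6 for one class, the related, serious, non-fatal suicidal event. This rests on reading 10.2 to 10.6 as written and is subject to the IRB and NIMH policies that are cited but not included.

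The document gives no attempt rate, so no number of misclassified or delayed events can be stated. It defines no SAE table either, so the effect on a reported SAE count is conditional on one being presented.

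A reader might also infer that such events go unrecorded or that no prompt report exists anywhere. Neither follows: the AE record, C-SSRS, Cornell Services Index, 24-hour expectation for SAEs and study-related-death route all remain. The SUS endpoint is unaffected. This should be corrected because it concerns oversight of the main anticipated harm in minors, but it falls short of a must-fix.

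**What to change.** Reconcile sections 9.1, 10.2, 10.4, 10.5 and 10.6:

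- Record three separate determinations on the eCRF: seriousness by the outcome list in 10.5; relatedness to any part of the program (website, support-adult contact, specialist contact, study procedures); and expectedness.
- Word 10.2, 10.4 and 10.6 so that the expected label alone does not take a related, serious suicidality event off the expedited route. If the cited policies already set a timeline for this class, state it in 10.6.
- State how completed suicide is classed and reported, and who receives the 24-hour SAE report.
- Prespecify a table of all suicide attempts, suicide-related hospitalizations and deaths regardless of attribution, drawn from the AE record, C-SSRS and Cornell Services Index.

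The cost is protocol wording, a few eCRF fields and one table. The downside is a few more SAE forms or expedited reports and a less favorable SAE count. No new data collection from participants is needed.

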10.6 REPORTING OF ADVERSE EVENTS

AEs which are unexpected, related, and serious will be reported to the Michigan Medicine IRB within 7 calendar days and to the NIMH PO within 10 business days. Death related to the study will be reported to the NIMH PO within 5 business days. All other AEs will be documented and reported to Michigan Medicine IRB and NIMH PO at the time of the respective annual progress reports.

10.7 REPORTING PERIOD

In this study, all adverse events are collected starting at the time informed consent has been signed. AEs are collected until the last study visit and exit from the study.

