4.2 DEFINITION OF END OF TRIAL

The end of trial is the date of the last visit/telephone follow up of the last participant. A participant is considered to have completed the study if they have completed the baseline assessment, all intervention tasks, and all follow-up assessments.

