Columbia-Suicide Severity Rating Scale (C-SSRS)	Adverse Events related to Suicidal Ideation and/or Behaviors	Adverse event monitoring will be assessed with the Columbia-Suicide Severity Rating Scale (C-SSRS). The C-SSRS is a semi-structured, rater-based interview to assess the severity and intensity of SI and behaviors (Mundt et al., 2013).
	Demographics, Contact, and Information Form	Interviewer will ask participants their age, gender identity, sex, race/ethnicity
	Medical Abstraction Form	Current psychiatric diagnoses will be obtained by reviewing admission reports and electronic medical records.
	Medication use	Youth medication use will be recorded using a combination of medical record review and parent/youth interview. The following information will be recorded for each medication: name, indication, dose, frequency, start, and end date.
Cornell Services Index (CSI)	Treatment Utilization	Treatment utilization will be assessed using the CSI, an interview-based method that assesses engagement in health treatment (e.g., outpatient psychotherapy, inpatient hospitalization).
Chronic Health Conditions Questionnaire (CHCQ)	Chronic Health Conditions	A 31-item questionnaire adapted from the National Survey of Children's Health (2022) to obtain current and past chronic health conditions and their severity among youth participants.
Adolescents' use of 'caring adult' support	Quality/Frequency of support	The Adolescents' use of 'caring adult' support will ask youth about their interactions with their support adults to better understand how they are using eYST for social support.
eYST platform measures	Youth concerns and support progress	Parents will provide information about current concerns for youth. Support persons will complete 12 weekly check-ins via the eYST platform to indicate progress with youth.

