10.8 SAFETY MONITORING AND REPORTING

PROPRIETARY AND CONFIDENTIAL

Oui Therapeutics, Inc. | [name]

Suicidal ideation/behaviors and other clinical outcomes will be assessed at the Week 0 and Week 12 follow-up assessments. Week 0 is the study baseline assessment, which occurs while the participant is housed in an inpatient treatment facility. For purposes of risk management, results of the study assessment at Week 0 will be shared with the inpatient treatment team in order to provide information relevant to their treatment/discharge planning. The 12 week follow up assessment is conducted by phone. In order to facilitate risk management during study interview calls, we will do the following:

- 1) Only enroll participants who are able to provide at least one verifiable contact for emergency or tracking purposes;
- 2) Obtain location information at the start of each phone assessment; and
- 3) Schedule assessments at a time when the parent/guardian is present at the same location as the participant.

Each youth assessment session will begin by confirming via telephone/video whether the youth and guardian are together. Increases in suicide risk will be communicated to the parent/guardian and outpatient provider (see Appendix B). In addition, interviewers will engage in risk management interventions as clinically indicated following the guidelines outlined in the Risk Management Plan (see Appendix B). Participants will be informed that information they input to the digital platform is not monitored for purposes of risk assessment.

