12.2 ADDITIONAL CONSIDERATIONS

Staff training at study initiation

1. Trained/Designated Staff: There will be designated research staff who will be trained to collect study outcomes.

PROPRIETARY AND CONFIDENTIAL

Oui Therapeutics, LLC Aviva (OTX-2021)	Digital Youth-Nominated Support Team (YST) Program	Informed Consent Form Clean Copy Page 33
---	---	---

2. **Clear Definitions and Electronic Data Capture:** We will use a structured method for obtaining all study outcomes. For variables assessed, there will be clear definitions. Staff will receive training in how to apply those definitions and record them in the study electronic data capture (EDC) system.

During study monitoring and support

1. **Study Monitoring and Data Fidelity Checks:** The sponsor or its representative may visit the study facilities at any time (remotely and /or in person) in order to maintain current and personal knowledge of the study through review of the records, comparison with source documents, observation and discussion of the conduct and progress of the study. The clinical site will permit trial-related monitoring, audits, IRB/IEC review, and regulatory inspection(s) by providing direct access to source data/documents.
2. **Fidelity Checks:** As part of study monitoring, we will conduct ongoing fidelity checks for the primary outcomes (and other variables of interest). During fidelity checks, records will be pulled randomly. If errors in coding the variables are observed, the nature of the error will be evaluated to determine whether study procedures need to be updated to improve clarity (though unlikely as we are using methodologies established in prior work) and/or staff require additional training in how to capture the study variables.

Procedures for participants who drop out or are lost to follow-up

If subjects drop out or are lost to follow-up, there will be agreements with the subject per the Informed Consent that the research staff can access different sources of information other than medical records. Additional sources of information will be the persons listed as individuals the research staff may reach out to if the research staff cannot contact the participants. The study team may also attempt to obtain final study assessments if possible before withdrawal of consent, as previously mentioned in Section 9.2 Participant Discontinuation/Withdrawal From The Study.

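### After the PI withdraws a youth for harm, nothing requires collection of new adverse events separate from that harm, and the Week 12 C-SSRS becomes optional

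*Combined protocol and SAP*

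**What the plan says.** Section 9.2 lists the grounds on which the PI may withdraw a participant from the study. One covers participants who cannot be reached, "or are determined to be adversely affected by the program". The section heading names both discontinuation and withdrawal, but the text describes only withdrawal from the study. The one contact it mentions at that point is an optional exit interview about the participant's experience.

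On AE collection, section 10.2 states: "Adverse Events (AEs) will be monitored and documented at each study visit". Section 10.7 sets the end of the window: "AEs are collected until the last study visit and exit from the study". Section 10.4 adds: "Any study participation related adverse events are to be followed until there is evidence of resolution or permanent change".

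On suicidality, section 8.1 names the C-SSRS as the instrument for monitoring AEs of suicidal ideation and behavior. Section 10.8 gives its timing: "Suicidal ideation/behaviors and other clinical outcomes will be assessed at the Week 0 and Week 12 follow-up assessments". Table 1 agrees, with the youth C-SSRS at W0 and W12 only. Appendix B attaches its high-risk notification to the baseline and 3-month assessments.

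For participants who leave early, section 12.2 says: "The study team may also attempt to obtain final study assessments if possible before withdrawal of consent". It also allows staff, by agreement in the consent form, to use sources beyond the medical record, including contact persons whom the participant has listed.

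**The concern.** Section 10.1 states a safety hypothesis for eYST. A youth whom the PI judges to have been harmed by the program is among the most informative participants for it. Such a youth may still be reachable and willing, with consent and assent intact. The only route section 9.2 gives the PI is to remove that youth from the study, and required collection of new AEs then ends.

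At stake are events nobody is obliged to ask about: those separate from the harm that led to withdrawal, or those that start after it has resolved. Section 10.5 counts suicidal behavior as an SAE only if it is linked to use of the eYST website and also meets the SAE criteria. That judgment cannot be made on an event that was never collected. The scheduled measure of suicidality, and the risk check that goes with it, would also rest on staff discretion.

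**Working it through.** The plan states no figure to reproduce. The check sets the provisions side by side and counts scheduled contacts.

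**What is required after the PI withdraws a youth for harm, with consent and assent still in place**

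- *The AE that led to withdrawal.* It is participation-related by the terms of 9.2, so 10.4 requires it to be followed to its outcome. **Covered.**
- *A later attempt or readmission, where that AE was worsened suicidality.* Such an event shows that the AE has not resolved, so follow-up under 10.4 would normally bring it to light. **Normally covered.**
- *A sign of raised suicide risk that staff come to know of.* Appendix B requires prompt action. **Covered once known**, but this creates no contact at which it would become known. The regular risk-status review by the PI or a co-investigator checks whether status was correctly identified and recorded; it is not itself a contact with the youth.
- *A new AE unrelated to the original harm.* 10.4 governs AEs already identified, 10.2 works through study visits, and 10.7 closes at exit. **Not required.**
- *A new AE, including an attempt or readmission, that arises after the original harm has resolved.* 10.4 follow-up has ended and 10.7 has closed. **Not required.**
- *The W12 C-SSRS and the 3-month Appendix B check.* The sentence in 12.2 is permissive. It sits under participants who leave early or cannot be reached, and does not name PI withdrawal. It points back to 9.2 for this provision, but 9.2 has only the exit interview. **Optional at best.**

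**Counts per youth withdrawn for harm before W12**

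- Scheduled post-baseline C-SSRS (Table 1, 10.8): W12 only, so 1. Made optional: 1 of 1.
- Assessments after baseline to which Appendix B ties its high-risk notification: 3 months only, so 1. Made optional: 1 of 1.
- Youth instruments at W4 in Table 1: SUS, user feedback questions, FIM, AIM, IAM and CSQ-I = 6, of which 0 measure suicidality. W4 matters here only as a visit at which 10.2 has AEs documented.
- Scheduled youth contacts after baseline: W4 and W12 in Table 1, matching the youth payments in 8.7. Contacts remaining are 2 if withdrawal comes before W4 and 1 if it comes after.
- Each such youth is 1/20 = 5% of the planned youth sample (section 7).

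The SIQ-JR and the parent-reported Cornell Services Index are also scheduled in Table 1 only at W0 and W12, so neither fills the interval.

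**The case against.** The strongest reply is that 10.4 already does most of the work. The scenario begins with a harm attributed to the program, and 10.3 and 10.4 anticipate mainly suicidality and suicide-related hospitalization. Where that is the harm, mandatory follow-up would normally reveal a later attempt or readmission. This stands. A reader might infer that the plan stops looking at a harmed youth altogether; 10.4 and Appendix B do not support that reading. What survives is narrower: events separate from the original harm, events after it resolves, and the scheduled W12 assessment.

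Second, the wording of 10.7 could leave collection open if a withdrawn youth still attended at Week 12, and the listed contact persons in 12.2 could supply collateral information. Both are possible, but neither carries a duty to collect AEs or a time at which to do so.

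Third, the answer may lie elsewhere. Section 13.2 refers to a data safety and monitoring plan, and 10.2 defers AE reporting to IRB and NIMH policy. Those documents, the consent form, and the protocol text between sections 16 and 18 were not available for this review. This stands as a limit on the conclusion.

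Three further inferences would go too far. A reader might take the definition of a completer in 4.2 to bar follow-up after eYST stops; it only says who counts as having completed. A reader might count the weeks between withdrawal and Week 12 as lost surveillance; AEs are documented at visits, and at most two youth visits remain after baseline. A reader might conclude that an extra C-SSRS is needed when eYST stops; that would exceed what any other youth has scheduled between W0 and W12, in a youth already judged harmed, and is better left to clinical judgment.

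**Conclusion.** The point holds in limited form and is a cheap improvement. On the available text, PI withdrawal for harm before Week 12 removes any requirement to collect new AEs that are separate from the original harm or follow its resolution. It also makes optional the one scheduled post-baseline C-SSRS and the one post-baseline Appendix B check tied to it.

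This rests on two assumptions: that withdrawal under 9.2 counts as exit for 10.7, and that no unseen document sets post-withdrawal safety follow-up. If the 12.2 sentence does not extend to PI withdrawal, there is no stated provision for a final assessment at all.

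The number of youths affected is unknown. The plan gives no withdrawal rate, none is assumed here, and among 20 youths it may be zero. A reader might infer a biased safety or outcome estimate. The documents give no basis for the size or direction of such a bias, and 12.1.3 already declines conclusive statements about intervention effects. The issue is completeness of safety information on a few youths.

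**What to change.** **Section 9.2.** Distinguish *discontinued from eYST* from *withdrawn from the study*. When the PI stops eYST for harm and neither consent nor assent has been withdrawn, keep the contacts already scheduled: AE questions at each remaining visit and the W12 phone C-SSRS, with the Appendix B criteria applied to it. Allow a clinician to waive the C-SSRS if it would cause distress, with AE information then taken from the parent. Leave any C-SSRS at the time of stopping to clinical judgment. The grounds for stopping eYST stay with the investigators. This would also give the cross-reference in 12.2 something to point to.

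**Section 10.7.** End collection of new AEs at the W12 assessment or at withdrawal of consent, and state that known participation-related AEs continue to be followed as in 10.4.

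**Cost.** Wording in two sections and no new visit, since the W12 phone assessment is already planned. The downside is continued contact with a few youths, and possible distress from suicide-focused questions, a risk that 2.3.1 recognizes. The opt-out limits it.
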